#### **9.1.2 Definition of Missing Data Imputation**

##### **Non-Responder Imputation (NRI) Approach**

The NRI approach will categorize any subject who has a missing value for categorical variables at a specific visit as non-responder for that visit. In addition, subjects who prematurely discontinue from study drug will be considered as non-responders for all subsequent visits after discontinuation.

### **Observed Cases (OC)**

The OC analysis will not impute values for missing evaluations. In addition, the OC will not use values after premature discontinuation of study drug. This sensitivity analysis will only be applied to the analysis prior to treatment switching.

### **As Observed (AO)**

The AO analysis will not impute values for missing evaluations. Regardless of treatment switching or premature discontinuation of study drug, all observed data will be used in the analysis. The AO analysis will be applied to long-term efficacy analysis.

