#### **Period 2**

To evaluate the long-term safety, tolerability, and efficacy of upadacitinib 30 mg QD and 15 mg QD in subjects with RA who have completed Period 1.

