### **Long-Term Efficacy Analysis**

Long-term efficacy analysis will be performed on As Observed data (defined in Section 9.1.2) by randomized treatment group sequence as described below:

1. Placebo → Upadacitinib 15 mg QD
2. Placebo → Upadacitinib 30 mg QD
3. Upadacitinib 15 mg QD
4. Upadacitinib 30 mg QD

There will be no statistical testing; only descriptive statistics and confidence intervals will be provided.

Starting with Amendment 4, all subjects will receive open-label upadacitinib 15 mg QD, including those currently on upadacitinib 30 mg QD. For long-term efficacy analysis, subjects will continue to be summarized under the treatment sequences as described above, regardless of dose switch – i.e., for treatment sequences 2 and 4, data collected after dose switch will continue to be summarized under the same treatment sequences. The visit at which dose switch occurs could be different for each subject. The first and last visits at which dose switch occurs will be noted in the summary.

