### **MMRM and Generalized Linear Mixed Model (GLMM) for Long-Term Analysis**

The repeated measure analysis will be conducted using mixed model including As Observed measurements at all visits. MMRM will be used for continuous endpoints and GLMM will be used for binary endpoints. The mixed models will include the categorical fixed effects of treatment, visit and treatment-by-visit interaction, and main stratification factor prior bDMARD use. For the MMRM analysis of change from baseline in continuous endpoints, the baseline measurement will be included as a continuous fixed covariate. The categorical fixed effect of subject's discontinuation status may also be

included in the model as appropriate. Unstructured, Toeplitz, compound symmetry, or other covariance structures may be considered.

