### **Multiple Imputation (MI)**

The MI analysis will impute missing data multiple times under appropriate random variation and thus generate multiple imputed "pseudo-complete" datasets. Results will be aggregated across the multiple imputed datasets, overcoming drawbacks of the single imputation methods. LOCF will be first applied to augment data into monotonic missing pattern and PROC MI will be used to generate 5 datasets using the regression method. Specifically, visits will be imputed in order, where later visits are imputed by regressing upon all previous visits, baseline, treatment group, demographics and other key baseline characteristics. Analysis will first be performed on each of the multiple imputed datasets, and PROC MIANALYZE will then be used to aggregate the results for the final statistical inference. The imputation is based on the assumption of data being missing at random. The missing at random assumption is considered reasonable given the high placebo response rate typically seen in RA trials. Additionally in RA trials, the proportion of discontinuation is relatively small (10 – 15% only) and the rate of discontinuation due to lack of efficacy is generally low (< 5%).

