### 9.3 Long-Term Efficacy Analysis

Assessments to evaluate long-term efficacy will be analyzed for the following measures at Week 1, 2, 4, 8, 12, 24, 36, 48, every 12 weeks through Week 240, and at Week 260.

- ACR20/50/70 response rates;
- Change from baseline in individual ACR components;
- Change from baseline in DAS28 (CRP);
- Change from baseline in DAS28 (ESR);
- Change from baseline in CDAI;
- Change from baseline in SDAI;
- Change from baseline in morning stiffness (severity and duration);
- Proportion of subjects achieving LDA and proportion of subjects achieving CR based on DAS28 (CRP), DAS28 (ESR), SDAI, and CDAI criteria;
- Proportion of subjects achieving MCID in change from baseline in HAQ-DI (defined as change from baseline in HAQ-DI  $\leq -0.3$ );

- ACR/EULAR Boolean remission;
- Proportion of subjects with no concomitant corticosteroid use (among subjects with corticosteroid use at baseline).

Assessments to evaluate long-term efficacy will be analyzed for the following measures at Week 4, 12, 24, 48:

- Change from baseline in EQ-5D-5L;
- Change from baseline in ISI (sleep);
- Change from baseline in SF-36.

Analyses will be based on As Observed (AO) data. Descriptive statistics will be provided for each randomized treatment group sequence as defined in Section 9.1.1. These include the number of observations, mean, standard deviation, and 95% CI for continuous endpoints; and frequencies and percentages with 95% CI using normal approximation for binary endpoints. In addition, longitudinal analysis will be performed using MMRM or GLMM as described in Section 9.1.2 for all endpoints except proportion of subjects with no concomitant corticosteroid use. Point estimates and 95% CI from the model will be provided for each treatment group sequence. Plot for each randomized treatment group sequence over time will be provided.

For the purpose of Period 1 CSR, response rate and 95% CI using NRI for binary endpoints will be provided for each randomized treatment group sequence by visits up to Week 24. For continuous endpoints, the LS mean and 95% CI based on MMRM will be reported for each randomized treatment group sequence by visits up to Week 24.

Table 5 below provides the overview of the long-term efficacy analyses to be performed on different endpoints.

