# Key endpoints for figures include: ACR20/50/70, LDA and CR based on DAS28(CRP) and CDAI criteria, Boolean remission, change from baseline in DAS28(CRP) and CDAI.

Note: NRI for binary endpoints and MMRM for continuous endpoints were used for analysis up to Week 24, as described in this section. The analyses had been completed prior to SAP Version 3.0 and is no longer mentioned in [Table 5](#) for streamlined summary of future long-term efficacy analysis.

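### After Week 24 every planned disease-response analysis includes values collected after study drug is stopped, and no on-drug or non-responder summary is specified beside it

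*SAP*

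**What the plan says.** The Period 2 objective (protocol 4.0), for those finishing Period 1, is "To evaluate the long-term safety, tolerability, and efficacy of upadacitinib 30 mg QD and 15 mg QD in subjects with RA". SAP 9.1.1 has long-term efficacy "performed on As Observed data (defined in Section 9.1.2) by randomized treatment group sequence", and SAP 9.1.2 defines AO so that "Regardless of treatment switching or premature discontinuation of study drug, all observed data will be used in the analysis". SAP 9.3 and Table 5 apply AO to the long-term binary and continuous endpoints through Week 260.

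Two other rules in SAP 9.1.2 treat off-drug values differently, and both end early:
- Observed Cases (OC) drops values after study drug is stopped, but "This sensitivity analysis will only be applied to the analysis prior to treatment switching", that is, up to Week 12.
- Non-responder imputation (NRI) sets subjects to non-response after they stop. By sequence it is limited to the Period 1 report: rates and intervals "using NRI for binary endpoints will be provided for each randomized treatment group sequence by visits up to Week 24". The note to Table 5 confirms this: "NRI for binary endpoints and MMRM for continuous endpoints were used for analysis up to Week 24, as described in this section". It adds that this work is complete and is left out of the table for future reporting.

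The long-term MMRM and GLMM are fitted to the same AO data. On stopping, the SAP offers only an option: "The categorical fixed effect of subject's discontinuation status may also be" included as appropriate. Appendix B (COVID-19) keeps those models and adds no on-drug analysis.

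**The concern.** Off-drug values are built into the design. Protocol 5.1 asks that subjects who stop study drug keep attending the scheduled visits and leaves their treatment to the investigator. Protocol 6.1.7 recognises that they may be on standard-of-care therapy. From Week 24, a subject whose tender and swollen joint counts have not both improved by a fifth over baseline at two visits in a row, despite optimized background therapy, must stop study drug (protocol 5.1 and 5.4.1). If that subject later responds to a different drug, AO shows a responder in an upadacitinib sequence.

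SAP 7.0 also allows subjects to enter Period 2 participation after stopping drug in Period 1. A placebo subject who stopped before Week 12 and stayed in follow-up would be summarized in a placebo-to-upadacitinib sequence without having taken upadacitinib.

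At stake is how the long-term rates are read. A by-visit response rate labelled with an upadacitinib sequence mixes response on the drug with response after it, and no table shows how much of each is present. The SAP handles long-term safety differently: treatment-emergent events stop 30 days after the last dose (10.2), and long-term event rates follow the treatment actually received (10.2.2). Efficacy has no counterpart.

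**Working it through.** **Plan's own figure.** None is stated for Period 2 efficacy. The power statement (SAP 4.3) concerns Week 12 only and does not bear on this point.

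**Step 1: which rule covers disease response after Week 24?**

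| Rule | Values after stopping study drug | Last visit covered |
|---|---|---|
| OC | excluded | Week 12 |
| NRI by sequence | set to non-response | Week 24 |
| AO descriptive | kept | Week 260 |
| Long-term MMRM/GLMM | kept (AO data) | Week 260 |

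After Week 24 only the last two rows remain, and both keep off-drug values. The optional discontinuation term does not fill the gap. The SAP does not say whether it means stopping drug or leaving the study, and it plans no on-drug estimate from it.

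**Step 2: how far apart could the summaries be?** The documents give no Period 2 off-drug share, so these inputs are borrowed and illustrative:
- f, the off-drug share of those observed at a visit: 5% to 15%. SAP 9.1.2 puts discontinuation for lack of efficacy in RA trials generally below 5%, and all discontinuation at 10% to 15%.
- r, the ACR20 rate in those subjects: 27% to 47%, the planned Week 12 placebo rate and that rate plus the planned 20-point difference (SAP 4.3).
- p, the on-drug ACR20 rate: 73%, the highest Phase 2 rate in TNF-IR subjects (protocol 3.0).

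Formulas:
- AO = (1 − f)p + f·r
- Count-as-failure among those observed, CF = (1 − f)p
- On-drug = p
- AO − CF = f·r; AO − on-drug = f(r − p); on-drug − CF = f·p

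| f | r | CF | AO | AO − CF | AO − on-drug |
|---|---|---|---|---|---|
| 5% | 27% | 69.35% | 70.70% | +1.35 | −2.30 |
| 5% | 47% | 69.35% | 71.70% | +2.35 | −1.30 |
| 15% | 27% | 62.05% | 66.10% | +4.05 | −6.90 |
| 15% | 47% | 62.05% | 69.10% | +7.05 | −3.90 |

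On-drug − CF is 0.05 × 73 = 3.65 points and 0.15 × 73 = 10.95 points. The sign of AO − on-drug depends on r − p. If subjects on a new therapy respond at more than 73%, AO rises above the on-drug rate.

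**Step 3: subjects no longer observed.** CF above covers only observed subjects. A non-responder analysis of all subjects also counts as failures those who stopped drug and left, so its gap to AO is wider. Let q be the share of all subjects who stopped drug and a the share of those still assessed, and assume everyone on drug is observed:
- AO = [(1 − q)·p + q·a·r] / [(1 − q) + q·a]
- NRI = (1 − q)·p

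Take p = 70%, r from 27% to 70% and a from 25% to 100%, all assumed:
- q = 15%: NRI = 0.85 × 70 = 59.5%. AO runs from 59.5 + 0.15 × 27 = 63.55% (a = 1, r = 27%) to 70.0%.
- q = 30%, also assumed: NRI = 49.0%. AO runs from 49.0 + 0.30 × 27 = 57.1% to 70.0%.

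**Step 4: precision.** At 73%, the 95% half-width is 1.96 × √(0.73 × 0.27 / n): 7.1 points at n = 150 and 10.0 at n = 75, the planned sequence sizes.

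**The case against.** The strongest reply is that AO is a deliberate treatment-policy choice. Off-drug follow-up is there to reduce missing data, and AO uses it. Period 2 is descriptive with no testing, and its objective does not say *while on drug*. That stands: AO is not an error and should remain the main summary.

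An on-drug rate also has its own defect. The Week 24 joint-count rule takes persistent non-responders off study drug, and both counts are required for ACR20, so the protocol itself enriches the on-drug set for responders. This stands too, and is why an on-drug rate should not be shown alone.

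The size is not wholly unknowable. SAP 7.0 reports Period 2 discontinuation of drug and of participation separately, SAP 8.1 tabulates cumulative exposure, and SAP 9.3 reports numbers observed. Together these partly bound the off-drug share, but they do not give it by visit or show who is on a new therapy.

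The illustrative inputs are weak. The discontinuation figures are general RA-trial rates used to justify missing at random, not Period 2 off-drug shares, and the true share could be near zero or above 15%. The response rates come from Week 12. Every gap between AO and a companion rate in step 2 is also no larger than the 7.1-point half-width. That limits how much the illustration proves, although a difference in what is being estimated is not removed by sampling error.

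A reader might go further and infer that all efficacy reporting after Week 24 mixes in off-drug values. The corticosteroid-free endpoint may be an exception, because SAP 6.3 counts concomitant medication only to one day after the last dose. It is not a disease-response measure.

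A reader might also see a conflict between the ban on RA biologics throughout both periods (protocol 5.2.3.2) and off-drug treatment at the investigator's judgment (5.1). That is a separate wording matter, and this point needs no protocol change.

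**Conclusion.** The point holds as a cheap improvement. After Week 24 no pre-specified analysis of disease response separates time on upadacitinib from time after it, and none counts stopping as failure. AO alone therefore does not show response while on upadacitinib.

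It would be too strong to say that Period 2 has no valid efficacy estimate, or that AO overstates the drug. AO validly describes the randomized sequences. It lies at or above a count-as-failure rate by construction, but may lie below or above an on-drug rate. Week 12 inference, and by-sequence binary results through Week 24, are not affected.

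No document figure fixes the size. Under the borrowed inputs (5% to 15% of observed subjects off drug, their response 27% to 47%, on-drug response 73%), AO is about 1 to 7 points above count-as-failure and about 1 to 7 points below on-drug. This is an illustration, not a bound. Reporting the off-drug share would settle it.

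**What to change.** Amend SAP 9.1.2, 9.3 and Table 5 for future long-term reporting, which is all that version 3.0 governs (SAP 11.1). Keep AO as the main summary and add, as supportive:

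1. **On-drug analysis.** Exclude values after study drug discontinuation, but keep a premature-discontinuation visit held within 14 days of the last dose and before any new RA therapy, so that the visit recording failure is not lost. For the two 30 mg sequences, also censor at the switch to 15 mg; SAP 9.1.1 otherwise keeps 15 mg data in them.
2. **Non-responder analysis, binary endpoints.** Count subjects as non-responders at all visits after study drug discontinuation.
3. **Counts by visit and sequence.** Give the number of AO observations that are off drug, and the number on a new bDMARD or JAK inhibitor.

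State in the SAP that (1) is enriched for responders because the protocol removes joint-count non-responders from study drug from Week 24, and that it must be read beside (2) and AO.

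The cost is some extra tables and a more complex presentation. No new data are needed: medications are recorded with dates (protocol 5.2.3), the last-dose date is sought (5.4.1), and the underlying exclusion and non-responder rules are already defined in SAP 9.1.2.

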### **Mixed Effect Model Repeat Measurement (MMRM) for Short-Term Analysis**

The repeated measure analysis will be conducted using mixed model including observed measurements at all visits. The mixed model includes the categorical fixed effects of treatment, visit and treatment-by-visit interaction, main stratification factors at randomization and the continuous fixed covariates of baseline measurement. An unstructured variance covariance matrix will be used. The parameter estimations are based on the assumption of data being missing at random and using the method of restrictive maximum likelihood (REML). The missing at random assumption is considered reasonable given the high placebo response rate typically seen in RA trials. Additionally in RA trials, the proportion of discontinuation is relatively small (10 – 15% only) and the rate of discontinuation due to lack of efficacy is generally low (< 5%).

### **MMRM and Generalized Linear Mixed Model (GLMM) for Long-Term Analysis**

The repeated measure analysis will be conducted using mixed model including As Observed measurements at all visits. MMRM will be used for continuous endpoints and GLMM will be used for binary endpoints. The mixed models will include the categorical fixed effects of treatment, visit and treatment-by-visit interaction, and main stratification factor prior bDMARD use. For the MMRM analysis of change from baseline in continuous endpoints, the baseline measurement will be included as a continuous fixed covariate. The categorical fixed effect of subject's discontinuation status may also be

included in the model as appropriate. Unstructured, Toeplitz, compound symmetry, or other covariance structures may be considered.

### **Multiple Imputation (MI)**

The MI analysis will impute missing data multiple times under appropriate random variation and thus generate multiple imputed "pseudo-complete" datasets. Results will be aggregated across the multiple imputed datasets, overcoming drawbacks of the single imputation methods. LOCF will be first applied to augment data into monotonic missing pattern and PROC MI will be used to generate 5 datasets using the regression method. Specifically, visits will be imputed in order, where later visits are imputed by regressing upon all previous visits, baseline, treatment group, demographics and other key baseline characteristics. Analysis will first be performed on each of the multiple imputed datasets, and PROC MIANALYZE will then be used to aggregate the results for the final statistical inference. The imputation is based on the assumption of data being missing at random. The missing at random assumption is considered reasonable given the high placebo response rate typically seen in RA trials. Additionally in RA trials, the proportion of discontinuation is relatively small (10 – 15% only) and the rate of discontinuation due to lack of efficacy is generally low (< 5%).

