## **8.2 Determination of Sample Size**

The planned total sample size of 450 can provide approximately 90% power to detect a 20% difference in ACR20 rates (assuming a placebo ACR20 response rate of 27%), at two-sided  $\alpha = 0.025$  and accounting for 10% dropout rate. This sample size also provides approximately 90% power for a 17% difference in DAS28 LDA response rate (assuming a placebo DAS28 LDA response rate of 12%), at two-sided  $\alpha = 0.025$  and accounting for 10% dropout rate. It can also provide at least 90% power for most key secondary endpoints, at two-sided significance level of 0.025 and accounting for a 10% dropout rate.

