## **4.3 Sample Size**

The planned total sample size of 450 can provide approximately 90% power to detect a 20% difference in ACR20 rates at Week 12 (assuming a placebo ACR20 response rate of 27%), at two-sided  $\alpha = 0.025$  and accounting for 10% dropout rate. This sample size also provides approximately 90% power for a 17% difference in DAS28 (CRP) LDA response rate at Week 12 (assuming a placebo DAS28 LDA response rate of 12%), at two-sided  $\alpha = 0.025$  and accounting for 10% dropout rate. It can also provide at least 90% power

for most key secondary endpoints, at two-sided significance level of 0.025 and accounting for a 10% dropout rate.

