## **9.2 Efficacy Analysis by Week 12**

### **9.2.1 Primary Efficacy Analysis**

The primary endpoint for US/FDA regulatory purposes is ACR20 response at Week 12. The primary endpoint for EU/EMA regulatory purposes is LDA (based on DAS28 (CRP)  $\leq 3.2$ ) at Week 12. Analyses will be conducted separately for US/FDA regulatory purposes and EU/EMA regulatory purposes; for each set of analysis, only one primary endpoint is specified.

Analysis of the primary endpoint will be conducted on the FAS based on randomized treatment groups (Upadacitinib 15 mg QD, Upadacitinib 30 mg QD and the combined placebo groups). Point estimate and 95% CI using normal approximation will be

provided for the response rate for each randomized treatment group. Comparisons of the primary endpoint will be made between each Upadacitinib dose and the combined placebo group using the Cochran-Mantel-Haenszel test adjusting for stratification factor prior bMDARD use. Point estimate, 95% CI using normal approximation and p-value for the treatment comparison will be presented. Both the nominal p-value constructed using the Cochran-Mantel-Haenszel test and the adjusted p-value through the graphical multiplicity procedure described in Section 9.2.5 will be provided. For the primary analysis, non-responder imputation (NRI) will be used.

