### **9.2.3 Key Secondary Efficacy Analyses**

Ranked key secondary endpoints (at Week 12) for US/FDA regulatory purposes are:

1. Change from baseline in DAS28 (CRP);
2. Change from baseline in HAQ-DI;
3. LDA as measured by DAS28 (CRP);
4. Change from baseline in SF-36 Physical Component Score (PCS).

Ranked key secondary endpoints (at Week 12) for EU/EMA regulatory purposes are:

1. Change from baseline in DAS28 (CRP);
2. ACR20 response rate;
3. Change from baseline in HAQ-DI;

4. Change from baseline in SF-36 Physical Component Score (PCS).

Other key secondary endpoints (at Week 12) for both US/FDA and EU/EMA regulatory purposes are:

1. ACR50 response rate;
2. ACR70 response rate;
3. ACR20 response rate at Week 1.

For binary endpoints, frequencies and percentages will be reported for each randomized treatment group. Similar analyses as for the primary endpoint will be conducted.

For the major RA continuous endpoints DAS28 and HAQ-DI change from baseline, statistical inference will be conducted using analysis of covariance (ANCOVA) coupled with MI for missing data handling. Specifically, the ANCOVA model will include treatment as the fixed factor, and the corresponding baseline value and the stratification factor prior bDMARD use (Yes/No) as the covariates. For other continuous endpoints, statistical inference will be conducted using the MMRM model as described in Section 9.1.2, with the main stratification factor being prior bDMARD use (Yes/No). From both the MI and MMRM analyses, the LS mean and 95% CI will be reported for each randomized treatment group; the LS mean treatment difference and associated 95% CI and p-value will be reported comparing each Upadacitinib dose group with the combined placebo group. Both nominal p-value and adjusted p-value through the graphical multiplicity procedure described in Section 9.2.5 will be provided.

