### 9.2.5 Handling of Multiplicity

The overall type I error rate of the primary and ranked key secondary endpoints for the two doses will be strongly controlled using a graphical multiple testing procedure. Specifically, the testing will utilize the endpoint sequence of primary endpoint followed by the ranked key secondary endpoints in the order as specified in Section 9.2.3, and will begin with testing the primary endpoint using  $\alpha$  of 0.025 for each dose. Continued testing will follow a pre-specified  $\alpha$  transfer path which includes downstream transfer along the endpoint sequence within each dose as well as cross-dose transfer. Adjusted p-values for the primary and ranked key secondary endpoints will be provided based on the testing procedure.

[figure not shown]
The graphs for the testing procedures are provided in Figure 3 and Figure 4, for US/FDA and EU/EMA regulatory purposes respectively. In the graph, the arrows specify the  $\alpha$  transfer paths. Once an endpoint is rejected (i.e., deemed significant) at its assigned significance level, its significance level will be transferred to subsequent endpoint(s) following the arrow(s). The numbers on the arrows denote the weights for transferring significance levels. Specifically, the weight 1 denotes 100% transfer of significance level.

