**Table 4. Summary of Efficacy Variables and Corresponding Analyses for Efficacy Analysis by Week 12 (Continued)**

Efficacy Variables	Analysis Method
Key Secondary Variables (Continued)	
Continuous Endpoints: 
 
• Change from baseline in DAS28(CRP) at Week 12
 
• Change from baseline in HAQ-DI at Week 12
 
	
 
• LS mean, and 95% CI within each treatment group and LS mean, 95% CI and p-values between each Upadacitinib dose group and the combined placebo group using ANCOVA model with treatment, prior bDMARD use and baseline value as covariates. Both nominal p-value and adjusted p-value through the graphical multiplicity procedure described in Section 9.2.5 will be provided.
 
• Imputation: MI
 
• Analysis Set: FAS
 

Change from baseline in SF-36 Physical Component Score (PCS) at Week 12	
 
• LS mean and 95% CI within each treatment group and LS mean, 95% CI and p-values between each Upadacitinib dose group and the combined placebo group using MMRM model with fixed effects of treatment, visit and treatment-by-visit interaction, prior bDMARD use and baseline value as covariate. Both nominal p-value and adjusted p-value through the graphical multiplicity procedure described in Section 9.2.5 will be provided.
 
• Analysis Set: FAS
 

Additional Variables (summarized at all visits up to Week 12)	
Binary Endpoints: 
 
• ACR20/50/70
 
• LDA and CR based on DAS28(CRP), DAS28 (ESR), SDAI, and CDAI criteria
 
• Proportion of subjects achieving MCID in change from baseline in HAQ-DI among those with baseline HAQ-DI <math>\geq 0.3</math>;
 
• ACR/EULAR Boolean remission;
 
	
 
• Point estimate and 95% CI of the response rate for each treatment group. The 95% CI will be based on normal approximation.
 
• Point estimate, 95% CI and p-value for the treatment comparison between each Upadacitinib dose group and the combined placebo group using the Cochran-Mantel-Haenszel test adjusting for stratification factor prior bDMARD use. Only nominal p-value will be provided, and the 95% CI will be based on normal approximation.
 
• Imputation: NRI for primary analysis and OC for sensitivity analysis
 
• Analysis Set: FAS
 

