**Table 4. Summary of Efficacy Variables and Corresponding Analyses for Efficacy Analysis by Week 12 (Continued)**

Efficacy Variables	Analysis Method
Additional Variables (summarized at all visits up to Week 12) (Continued)	
Continuous Endpoints: 
 
• Change from baseline in individual ACR components
 
• Change from baseline in DAS28 (CRP) and DAS28 (ESR)
 
• Change from baseline in CDAI and SDAI
 
• Change from baseline in morning stiffness (severity and duration)
 
• Change from baseline in EQ-5D-5L
 
• Change from baseline in ISI (sleep)
 
• Change from baseline in SF-36
 
	
 
• LS mean and 95% CI within each treatment group and LS mean, 95% CI and p-values between each Upadacitinib dose group and the combined placebo group using MMRM model with fixed effects of treatment, visit and treatment-by-visit interaction, prior bDMARD use and baseline value as covariate. Only nominal p-value will be provided.
 
• Analysis Set: FAS
 

- a. US/FDA regulatory purposes.  
 b. EU/EMA regulatory purposes.

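### The multiplicity-adjusted Week 12 analyses of DAS28 (CRP) and HAQ-DI rest on only 5 imputations; 100 or more would remove most of the avoidable seed noise at almost no cost (low priority)

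*SAP*

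**What the plan says.** The multiple-imputation paragraph of SAP 9.1.2 first applies LOCF to reach a monotone missing pattern, and then says "PROC MI will be used to generate 5 datasets using the regression method". The results are pooled with PROC MIANALYZE. Protocol 8.1.4.1.5 names MI as the primary approach for key continuous endpoints but gives no number of imputations. Neither document gives a seed or a reason for choosing 5.

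SAP 9.2.3 bases inference for change in DAS28 (CRP) and HAQ-DI on "analysis of covariance (ANCOVA) coupled with MI for missing data handling". Both are ranked key secondary endpoints in the US and EU sequences. SAP 9.2.5 adds that "Adjusted p-values for the primary and ranked key secondary endpoints will be provided based on the testing procedure", starting at 0.025 per dose. Table 4 repeats this for the two endpoints: "Both nominal p-value and adjusted p-value through the graphical multiplicity procedure described in Section 9.2.5 will be provided". SF-36 PCS is analysed with MMRM instead. The primary endpoints do not use MI: "For the primary analysis, non-responder imputation (NRI) will be used" (SAP 9.2.1).

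**The concern.** With so few imputations, the pooled estimate and its standard error both vary from one random seed to the next. These two tests are confirmatory, and the SAP does not fix a seed, so the reported p-value cannot be regenerated from the plan. If a p-value fell near its assigned level, the seed could decide whether the endpoint is declared significant.

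The issue is reproducibility, not bias. Type I error is not at stake.

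**Working it through.** **Inputs from the documents.** Imputations m = 5 and discontinuation of 10–15% in RA trials (SAP 9.1.2); 150 subjects per upadacitinib arm and 150 in combined placebo (SAP 4.2); 10% dropout, two-sided α = 0.025, ACR20 27% vs 47% and LDA 12% vs 29% (SAP 4.3).

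**Assumption.** The fraction of missing information (FMI) for the treatment contrast is not documented. I take 5–10%, with 15% as the upper case. As a check, simulated 3 × 150 trials with monotone dropout of 5%, 10% and 15%, sequential-regression MI and ANCOVA gave mean FMI of 0.04, 0.09 and 0.12.

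**1. The plan's own power.** With 150 × 0.9 = 135 evaluable per arm, power for ACR20 is 88.3% (pooled variance) or 89.2% (unpooled). For LDA it is 89.4% or 90.3%. The stated figure of about 90% reproduces. The plan gives no Monte Carlo error for the MI.

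**2. Noise in the estimate.** In standard-error units, the Monte Carlo SD of the pooled estimate is √(FMI/m), and relative efficiency is 1/(1 + FMI/m). At FMI 10% the SD is √(0.10/5) = 0.141 against √(0.10/100) = 0.032. The ratio is √20 = 4.47 at any FMI, so m = 100 removes 1 − 1/4.47 = 78% of the SD and 1 − 1/20 = 95% of the variance.

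**3. Noise in the p-value.** With total variance 1 at unlimited m, draw the estimate from N(z, FMI/m) and B = FMI × χ²(m−1)/(m−1). Set T = (1 − FMI) + (1 + 1/m)B and use Rubin's df (m−1)(1 + 1/r)², where r = (1 + 1/m)B/(1 − FMI). The table takes a limiting p of 0.025 and 400,000 seeds per cell.

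| FMI | SD of estimate, m=5 / m=100 | Relative efficiency, m=5 | 95% range of p, m=5 | 95% range of p, m=100 |
|---|---|---|---|---|
| 5% | 0.100 / 0.022 | 99.0% | 0.015–0.045 | 0.022–0.028 |
| 10% | 0.141 / 0.032 | 98.0% | 0.011–0.061 | 0.021–0.030 |
| 15% | 0.173 / 0.039 | 97.1% | 0.009–0.080 | 0.020–0.032 |

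At a limiting p of 0.020 and FMI 10%, 37% of seeds exceed 0.025 with m = 5, against 1% with m = 100. At a limiting p of 0.001 and FMI 10%, the m = 5 range is 0.0003–0.005 and the verdict is in effect fixed.

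**4. How likely a p-value near the threshold is.** LDA is a cut of the DAS28 (CRP) score. If scores are normal with equal SD, the planned rates imply a difference of Φ⁻¹(0.29) − Φ⁻¹(0.12) = 0.622 SD. Then z = 0.622 × √(135/2) = 5.11, and power at two-sided 0.025 is 99.8%. For HAQ-DI no effect size or SD is given. Protocol 8.2 says only "It can also provide at least 90% power for most key secondary endpoints".

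**5. Chance that two seeds give different verdicts** (%, m = 5 / m = 100; 2,000,000 trials per cell):

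| Power | FMI 5% | FMI 10% | FMI 15% |
|---|---|---|---|
| 90% | 2.30 / 0.47 | 3.81 / 0.69 | 5.40 / 0.91 |
| 99% | 0.36 / 0.07 | 0.64 / 0.11 | 1.00 / 0.14 |
| 99.8% | 0.09 / 0.02 | 0.17 / 0.03 | 0.28 / 0.04 |

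**6. Conditioning on the EU sequence.** There LDA must be rejected before DAS28 (CRP) is tested. In 200,000 patient-level trials with 135 per arm, disagreement at m = 5 then falls to 0.02–0.04% (FMI 5–10%). With active-arm SD 0.8 times placebo it is about 0%. With 1.2 times placebo, DAS28 power drops to 94% and disagreement is 1.1–1.9%, against 0.2–0.3% at m = 100.

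**The case against.** The strongest reply is that no analysis still to be run is affected. SAP 11.1 and 12.0 record that the primary analysis and Period 1 reporting were done under Version 2.0, and Appendix B dates them to 2017. Version 3.0 governs long-term reporting, which uses As Observed data, MMRM and GLMM, with no MI. This stands. It limits the remedy but does not make m = 5 a better choice.

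Second, where the effect can be calculated it is negligible. For DAS28 (CRP) this is right, and baseline adjustment in the ANCOVA probably takes power above 99.8%. The 90% and 99% rows are scenarios for HAQ-DI, not trial figures, and the 1.2 SD ratio is only a sensitivity case.

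Third, a trial uses one seed, so the fairer comparison is with the verdict at unlimited m. On that measure, disagreement at m = 5 and FMI 5–10% is 1.6–2.7% at 90% power and 0.06–0.12% at 99.8%. The lower figures are fair, and the conclusion is the same.

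Fourth, a check without a seed is already planned: MMRM for DAS28 (CRP) and the ACR components, which include HAQ-DI. For these, Table 4 says "Only nominal p-value will be provided". A seed-driven MI result would be visible beside it, but the MI p-value remains the adjusted one.

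Fifth, the choice of 100 is conventional. At 90% power, m = 20 already reduces two-seed disagreement to 1.1–1.6%. That is true, but the further imputations cost almost nothing.

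**Conclusion.** The point holds as a free improvement of low priority. Five imputations are valid and cost only about 1–3% in efficiency, or roughly 0.4–1.0 points of power in a 90% scenario. They also leave avoidable seed noise in two multiplicity-adjusted p-values, and m = 100 removes about 78% of its SD. It matters only if a p-value lies near its assigned level. That is unlikely for DAS28 (CRP) and cannot be assessed for HAQ-DI from the documents.

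The sizes rest on an assumed FMI of 5–15% and an assigned level of 0.025, which cross-dose transfer could raise. The DAS28 power also assumes normal scores with equal SD. I claim no effect on later endpoints, because the graphs in SAP Figures 3 and 4 are not available in the text I have.

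**What to change.** Specify at least 100 imputed datasets in place of 5, with a stated seed, wherever this MI text is used again.

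For this trial the change can no longer be pre-specified. Leave the Week 12 result as reported. Beside it, give an m = 100 run with its seed as a disclosed post hoc check, together with the seed of the m = 5 run. The LOCF step and the imputation model need not change for this purpose. More imputations do not address either of them, or the missing-at-random assumption.

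The cost is minutes of computing and one extra line in a table. No subjects or new data are needed.
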